#### Efficacy Analyses

The primary is the change in WOMAC before GAE to 12 months after GAE. All statistical tests and confidence intervals (CIs) will be two-sided with a nominal significance level of p < 0.05 (95% confidence). A linear mixed model (LMM) will be used to test for the mean change in WOMAC while adjusting for potential site-effects. The baseline and 12 month observations will be included in the model. The dependent variable will be the changes in WOMAC and the independent variables will be the WOMAC at baseline, baseline severity (moderate/severe arthritis), indicators of time (fixed effect  $\Delta$ ) and random intercepts for patient and site. The parameter  $\Delta$  corresponds to the mean change in WOMAC. A Wald-type test of  $\Delta = 0$  and 95% CI of  $\Delta$  will be calculated.

Secondary analyses will also include analyzing changes from baseline to other timepoints and between post-treatment timepoints using the same methods. The Kaplan-Meier curves will be used to analyze the time until WOMAC improvement is first observed (i.e. time to improvement). The Turnbull method will be used to estimate these curves while accounting for interval censoring (the clinical improvement event is only known to have occurred between the current and prior visit).

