## Rationale

The knee receives its blood supply from the genicular arteries, branches from the superficial femoral and popliteal arteries. Deliberate partial blockage of the genicular arteries (embolization) leads to reduction of the inflammatory response, with potential improvement in pain. Recently, Okuno and colleagues reported their experience with genicular artery embolization for patients with mild-to-moderate knee osteoarthritis. In their pilot study, 14 patients underwent embolization (7). No major adverse events were reported. There was a dramatic and rapid reduction in symptom and pain scores of patients.

In 2017, the same authors reported their results of genicular artery embolization performed on 95 knees in 72 patients (6). All patients had pain that was resistant to conservative treatment, such as oral nonsteroidal ant-inflammatory drugs, oral opioid agents, physical therapy, stretching, muscle strengthening, or intraarticular injection of hyaluronic acid. The distribution of local tenderness (indicating the presence of inflammation) was evaluated in all cases immediately before transcatheter arterial embolization and subdivided into eight areas to determine the key arteries to be treated. After selective catheterization of the appropriate genicular artery, imipenem/cilastatin sodium was used as the embolic material in 88 knees in 65 patients. Patients who had contraindications to imipenem/cilastatin (ie, a history of hypersensitivity or allergy to antibiotic agents or treatment with valproic acid) were treated with 75-µm Embozene microspheres instead (7 knees in seven patients).

Mean Western Ontario and McMaster Universities Osteoarthritis Index (WOMAC) pain scores decreased significantly from 12.1 at baseline to 6.2 at 1 month, 4.4 at 4 months, 3.7 at 6 months, 3.0 at 12 months, and 2.6 at 24 months after the first transcatheter arterial embolization procedure (all P < .001). The intent-to-treat clinical success rate at 6 months of follow-up was 86.3% (95% CI, 78%–92%). The mean total WOMAC score also decreased significantly from 43 at baseline to 24, 14.8, 11.2, 8.2, and 6.2 at 1, 4, 6, 12, and 24 months, respectively (all P < .001). The mean VAS score significantly decreased from 72 at baseline to 38, 29, 19, 13, and 14 at 1, 4, 6, 12, and 24 months, respectively (all P < .001). Patients reported a decrease in the dose of medication used and frequency of other treatments after the procedure.

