# 4. Study Design

This is a single-center, prospective, single arm investigational study to evaluate the safety of genicular artery embolization (GAE) for treatment of symptomatic knee osteoarthritis (OA). In addition, the improvement as part of efficacy will be reported. All subjects will have either failed or be intolerant to conservative management, and be ineligible for or refuse surgical intervention. Subjects will be considered enrolled in the study once they have provided informed consent and have been determined to meet all eligibility criteria. A total of 40 subjects will be enrolled in the single treatment arm of the study and will be followed for 12 months. The subjects will be stratified according to arthritis severity based on imaging, with 20 subjects allocated to mild-moderate arthritis based on x-ray (Kellgren-Lawrence x-ray grade 1-2), and with 20 subjects allocated to severe arthritis based on x-ray (Kellgren-Lawrence x-ray grade 3-4). The stratification will not be randomized, but each category will be limited to 20 patients.

The study will involve a screening period in which patient eligibility is determined. Once eligibility is confirmed, subjects will undergo GAE with Embozene microspheres (100 micron). Following treatment, subjects will return for follow-up visits at 1 week (± 4 days), 1 month (± 2 weeks), 3 months (± 2 weeks), 6 months (± 2 weeks), and 12 months (± 2 weeks) post-procedure. At these visits, subjects will complete the Western Ontario and McMaster Universities Osteoarthritis Index (WOMAC) score, and a visual analog scale (VAS) score, undergo a directed physical examination, and report any new adverse events (AEs). At 3 months of follow-up, subjects will also undergo knee x-ray. At the 12 month follow-up, subjects will also complete a patient-reported outcomes (PRO) and patient global impression of change (PGIC) questionnaire.

The primary objective of the study will be to assess safety via minor and major adverse events. Secondary objective will be improvement of OA symptoms as assessed by the WOMAC and VAS scores at each follow-up visit. Subjects will continue to be followed according to the institutional standard of care after they complete the 12-month study visit.

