# 5. Treatments and Assessments

Subjects will be treated with a genicular artery embolization (GAE) procedure performed with Embozene Microspheres. The microspheres will be delivered in a saline-contrast medium solution and will be delivered to the arteries supplying the areas of the subject's pain. A complete description of the technical protocol to be followed is provided in Appendix C.

After GAE, follow-up visits will take place at 1 week ( $\pm$  4 days), 1 month ( $\pm$  2 weeks), 3 months ( $\pm$  2 weeks), 6 months ( $\pm$  2 weeks), and 12 months ( $\pm$  2 weeks) from the date of treatment. Subjects who cannot present in person to the clinic at the 3, 6 or 12 month visit due to travel restrictions from the COVID-19 virus will conduct the follow-up visit over the phone. A schedule of study events and study flow chart are presented in Appendices A and B, respectively.

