#### 5.3 Visits 3-7: Post GAE Follow-Up

Subjects will have the following assessments performed:

- Physical examination including vital signs
- WOMAC and VAS questionnaires (at visits 4-7)
- Review of adverse events
- Knee MRI (at visit 5: 3 month follow-up). If patients cannot undergo MRI (e.g. pacemaker, significant claustrophobia), then CT of the knee without contrast will be performed.
- Knee x-ray (at visit 7: 12 month follow-up)

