# 6. Withdrawal of Subjects

Subjects will be informed that they have the right to withdraw from the study at any time for any reason, without prejudice to their medical care. The Investigator also has the right to withdraw patients from the study for any of the following reasons:

- Adverse Event
- Concurrent medical condition
- Patient unwillingness to comply with study requirements
- Patient death
- Other Investigator decision

If a patient is withdrawn or discontinued from the study, the reason for withdrawal will be recorded in the source documents and on the End of Study case report form (CRF). All patients withdrawn from the study will be encouraged to complete, if possible, all clinical evaluations scheduled for the 12-month follow-up visit. All adverse events will be followed as described in Section 7. Patients who are withdrawn from the study for any reason will not be replaced. The Principle Investigator may terminate the study at any time.

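### The 12-month WOMAC model leaves out the month 1, 3 and 6 scores, so it cannot correct bias, in either direction, if month-12 scores are lost for reasons tied to earlier response

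*Combined protocol and SAP*

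**What the plan says.** Safety is the primary objective (Section 2.1) and efficacy is secondary (Section 2.2). Within efficacy, Section 9 treats the WOMAC change from baseline to 12 months as the main analysis, using a linear mixed model.

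- **Data used.** "The baseline and 12 month observations will be included in the model".
- **Model form.** "The dependent variable will be the changes in WOMAC and the independent variables will be the WOMAC at baseline", together with baseline severity, time indicators and random intercepts for patient and site.
- **Other visits.** "Secondary analyses will also include analyzing changes from baseline to other timepoints and between post-treatment timepoints using the same methods". The interim scores also feed the time-to-improvement curves.
- **Collection.** Section 5.3 lists "WOMAC and VAS questionnaires (at visits 4-7", and Appendix A agrees: months 1, 3, 6 and 12.
- **Retention.** Section 6 says "All patients withdrawn from the study will be encouraged to complete, if possible, all clinical evaluations scheduled for the 12-month follow-up visit". Under Section 5, patients kept from the 3, 6 or 12 month visit by COVID-19 travel restrictions "will conduct the follow-up visit over the phone".

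The documents state no missing-data assumption, imputation method or sensitivity analysis for WOMAC.

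**The concern.** A patient who lacks a month-12 score may still have scores at months 1, 3 and 6, and these are informative about the missing value. The planned model does not use them. If patients who responded poorly by month 6 tend to lack month 12, the mean improvement is overstated. If patients who feel well stop attending, it is understated.

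The model description can be read in two ways: one change value per patient with baseline as covariate, or two score rows per patient with a patient random intercept. The interim scores are unused under both, so the point does not depend on which is meant.

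What is at stake is the size of the 12-month change and its confidence interval. In a single-arm study these are the main efficacy result that a reader will take away.

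**Working it through.** **1. Figure to reproduce.** There is none. The documents give no SD, correlation, effect size, power or dropout rate for WOMAC.

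**2. Inputs.** From the documents: n = 40 and the visit schedule. Assumed: baseline SD s0 = 15; follow-up SD s = 15 to 18; correlation with baseline r0 = 0.5; correlation between follow-ups rf = 0.6 to 0.9; m = 4 or 8 patients without month 12. Leavers are drawn with weight exp(b × z), where z is the standardised 6-month change. With b = 1, a patient 1 SD worse is e^1 = 2.7 times as likely to be missing, and about 80% of leavers come from the worse half.

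**3. Hand approximation.** In a large pool these weights shift the leavers' mean z by b. The part of the month-12 score not explained by baseline has covariance s²(rf − r0²) with the month-6 score. So the baseline-adjusted estimate is off by about

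b × m/(n − m) × s²(rf − r0²)/SDc, with SDc = √(s0² + s² − 2·r0·s0·s).

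For s = 15, SDc = √(225 + 225 − 225) = 15. The last factor is 225 × 0.35/15 = 5.25 at rf = 0.6, 225 × 0.50/15 = 7.50 at 0.75, and 225 × 0.65/15 = 9.75 at 0.9. Multiply by 4/36 or 8/32.

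**4. Simulation with 40 patients** (1,000 trials per setting, true change −18 points; maximum likelihood on baseline and month 12, compared with complete data). The table gives points of overstated improvement.

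| rf | By hand, s = 15 (4 / 8 missing) | Simulated, s = 15 | Simulated, s = 18 |
|---|---|---|---|
| 0.6 | 0.58 / 1.31 | 0.51 / 1.00 | 0.63 / 1.30 |
| 0.75 | 0.83 / 1.88 | 0.77 / 1.48 | 0.93 / 1.94 |
| 0.9 | 1.08 / 2.44 | 0.95 / 1.93 | 1.23 / 2.48 |

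The hand values run higher because drawing leavers from only 40 patients cannot shift their mean by a full SD. Range: 0.5-1.2 points with 4 missing, 1.0-2.5 with 8. A one-change model with baseline centred at the mean of all 40 gives the same bias.

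**5. Sensitivity to the assumptions.**
- Weaker selection (b = 0.5): 0.3-0.7 (4 missing) and 0.6-1.3 (8).
- Stronger selection (b = 2): 0.8-1.9 and 1.5-3.6.
- Reversed selection (b = −1): improvement understated by 0.5-1.3 and 1.1-2.4.
- Loss unrelated to outcome (b = 0): under 0.1.
- Baseline correlation 0.3-0.7, b = 1: 0.2-1.3 and 0.4-2.6.
- A wider grid (SD 10-20, correlation 0.5-0.7, 10-30% missing, log-odds 1-2 per SD): about 0.35-4.5.

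**6. Unadjusted completers' mean change.** The last factor becomes (rf·s² − 2·r0·s0·s + s0²)/SDc, which for s = 15 is 15 × rf: 9.0, 11.25 and 13.5. Times 4/36, this is 1.00, 1.25 and 1.50; simulated 0.88, 1.13 and 1.31. Over s = 15 to 18 the simulated range is 0.8-1.4 with 4 missing and 1.7-2.9 with 8.

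**7. Scale.** For the cited series the Rationale reports: "The mean total WOMAC score also decreased significantly from 43 at baseline to 24, 14.8, 11.2, 8.2, and 6.2". The 12-month fall is 43 − 8.2 = 34.8. As shares of that: 0.5/34.8 = 1.4%, 1.2/34.8 = 3.4%, 1.0/34.8 = 2.9%, 2.5/34.8 = 7.2%. The SE of the estimate is 2.4-3.0 points. With b = 1, nominal 95% coverage is 92-95% with 4 missing and 86-93% with 8. With a true change of 18 points, the test of no change was significant in every simulated trial.

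**8. All visits in one likelihood model.** When loss depends on observed scores, bias falls to within 0.1 point. If month 6 drives the loss but is itself missing, 0.05-0.22 (4 missing) or 0.16-0.51 (8) remains.

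**The case against.** The strongest reply is that the impact is small. This is a secondary objective in a safety study. With 4 missing, a bias of 0.5-1.2 points is well inside one SE on a 0-96 scale (20 + 8 + 68, Section 8.1), and the all-visit model lowers root mean squared error by only 4-9% (about 9-24% with 8 missing). Every driver of size is assumed, and an 80:20 split of leavers is not mild. Nothing in the documents predicts response-related loss, and the phone visits and the request to withdrawn patients work against it. All of this stands, and it limits the weight of the point. Retention measures reduce missing scores, however; they do not adjust for those that remain.

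Four stronger readings are tempting, and the documents do not support them:

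- **That the plan is tilted in favour of GAE.** The direction depends on who is lost, which the documents do not say.
- **That the plan adjusts for no missingness at all.** Baseline WOMAC and severity are in the model, so loss related to those can be handled.
- **That 0.8-1.4 or 1.7-2.9 points is the bias of the planned model.** Those figures apply only to an unadjusted completers' mean change, or to a model evaluated at the completers' baseline mean.
- **That the efficacy test or the safety result is in doubt.** The test is unlikely to change if the effect is large, and the adverse-event analyses do not use this model.

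**Conclusion.** The concern holds as an improvement of low to moderate impact. The scores most informative about a missing month-12 value are collected but excluded from the estimate, and nothing elsewhere in the plan makes up for it. The central size, 0.5-1.2 points with 4 of 40 missing and 1.0-2.5 with 8, rests wholly on the assumed SDs, correlations, loss rates and selection strength. The true figure could be zero or have the opposite sign. What is affected is the estimated change and the coverage of its interval. The lack of a control arm is a larger limit on the efficacy result, and this change does not address it.

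**What to change.** Replace the sentence that limits the model to two timepoints with:

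> All scheduled WOMAC observations (baseline and months 1, 3, 6 and 12) from all treated patients will be included in one likelihood-based (REML) repeated-measures model with WOMAC score as the dependent variable; categorical visit, baseline severity and severity-by-visit as fixed effects; unstructured covariance across visits (heterogeneous compound symmetry if it does not converge); and Kenward-Roger degrees of freedom. Baseline is an outcome row and not also a covariate. The month-12 minus baseline contrast, averaged over the severity strata in their enrolled proportions, with 95% CI, is the estimate.

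The severity-by-visit term lets the change itself differ by severity; a main effect alone would shift all visits equally.

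Edit the rest of the paragraph to match. Remove change as the dependent variable, the baseline covariate and the patient random intercept. Remove the site random intercept and the wording on site effects as well, since Section 4 describes a single-center study. Take the other timepoint contrasts from the same fit.

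Add:

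> The model assumes that month-12 scores are missing at random given the observed scores and severity. The number of patients without a month-12 score, and the reasons, will be reported. As a sensitivity analysis, missing scores will be multiply imputed using all WOMAC visits and severity, and imputed month-12 scores will be worsened by pre-stated deltas.

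Each delta moves the mean by (number missing/40) × delta. For illustration, 10 points moves it by 1.0 with 4 missing and 2.0 with 8.

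Before fixing the visit list, reconcile the schedule. Section 4, after listing visits that include week 1, says "At these visits, subjects will complete the Western Ontario and McMaster Universities Osteoarthritis Index (WOMAC) score", whereas Section 5.3 and Appendix A start WOMAC at month 1.

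**Cost.** SAP wording and slightly more analysis; no new data. Five visits need 5 × 6/2 = 15 covariance parameters from 40 patients, hence the small-sample correction. If no WOMAC score is missing, the estimated mean change is unaffected. The bias is removed only if loss depends on observed scores. About 20-80% remains if loss depends on the unseen month-12 score, which is why the delta analysis is needed. Under the fallback covariance, about a fifth to a third remains (0.1-0.35 points with 4 missing, 0.2-0.7 with 8).

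### The planned WOMAC model keeps the baseline rows and also adjusts for baseline WOMAC, so the 95% CI for the mean change is too narrow; its random site term cannot be estimated in a single-centre trial

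*Combined protocol and SAP*

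**What the plan says.** Section 9, Efficacy Analyses, names the main efficacy outcome: "The primary is the change in WOMAC before GAE to 12 months after GAE". It then sets out a linear mixed model with these parts:

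- Rows: "The baseline and 12 month observations will be included in the model".
- Response and covariates: "The dependent variable will be the changes in WOMAC and the independent variables will be the WOMAC at baseline, baseline severity", plus a time indicator whose coefficient is Delta.
- Random effects: "random intercepts for patient and site".
- Target: Delta "corresponds to the mean change in WOMAC", with a Wald-type test of zero and a 95% CI, two-sided at 0.05.

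The model is reused elsewhere: "Secondary analyses will also include analyzing changes from baseline to other timepoints and between post-treatment timepoints using the same methods".

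Section 4 describes the trial: "This is a single-center, prospective, single arm investigational study". It enrols 40 patients, 20 in each radiographic severity category. The documents do not mention a robust or paired standard error, or a covariance structure that would allow a negative patient variance.

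**The concern.** A mixed model on two rows per patient can reproduce the paired analysis exactly. It stops doing so once the first row is also used as a covariate. The baseline row then carries no information of its own: it equals the covariate if the response is the raw score, and it is zero if the response is the change. Adjustment removes between-patient variation from a model that relies on the patient intercept to separate between-patient from within-patient variation.

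What is at stake is the CI for Delta. In a single-arm trial with no efficacy threshold, the estimate and its interval are the efficacy result. The other baseline-to-visit contrasts use the same method and share the fault.

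The site term is a separate and smaller matter: the model includes a random effect for a factor that has one level.

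**Working it through.** **Inputs.** From the documents: n = 40, strata 20/20, one site, two rows per patient, two-sided 0.05. The plan states no WOMAC SD, correlation, SE or CI width, so there is no figure of its own to reproduce. Assumed: baseline SD 15; 12-month SD 7.5, 12, 15 or 18; baseline to 12-month correlation ρ = 0.3, 0.5 or 0.7; complete data; no true change for the type I error figures.

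**Notation.** Let d be the 12-month minus baseline WOMAC. SSd is the sum of squares of d about its mean, and RSS is the residual sum of squares of d after regression on baseline WOMAC and severity. R² is the share of var(d) that these two explain.

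**Step 1: the estimate.** Baseline WOMAC and severity are constant within a patient, so they drop out of the within-patient comparison. Delta is estimated by the mean of d. Its correct variance estimate is SSd/((n−1)n).

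**Step 2: the patient variance.** The within-patient part estimates the residual variance as var(d)/2. The patient means, after adjustment, have variance var(d)(1−R²)/4. The implied patient variance is

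var(d)(1−R²)/4 − var(d)/4 = −R²·var(d)/4,

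which is never positive. A random-intercept fit therefore usually sets it to zero. In simulation with equal SDs this happened in 99.8% / 98.7% / 91.9% of trials for ρ = 0.3 / 0.5 / 0.7.

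**Step 3: the planned SE.** With patient variance zero, both parts are pooled:

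SE² = (SSd + RSS)/((2n−4)n), where 2n−4 = 76.

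Relative to the correct SE this is about √(1 − R²/2). Raw score and change as response give the same SE.

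**Step 4: numbers.** With equal SDs, R² from baseline alone is (1−ρ)/2:

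- ρ = 0.3: R² = 0.35, √(1−0.175) = 0.91
- ρ = 0.5: R² = 0.25, √(1−0.125) = 0.94
- ρ = 0.7: R² = 0.15, √(1−0.075) = 0.96

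At ρ = 0.5, var(d) = 2·225·(1−0.5) = 225, so the true SE is 15/√40 = 2.37; the mean planned SE in simulation was 2.21. With the 12-month SD halved and ρ = 0.5, R² = 0.75 and the ratio is √(1−0.375) = 0.79.

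**Step 5: calibration.** 100,000 simulated trials per setting, Wald test with a z reference, for ρ = 0.3 / 0.5 / 0.7:

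| 12-month SD (baseline 15) | Planned SE / true SE | Type I error |
|---|---|---|
| 18 | 0.93 / 0.96 / 0.99 | 7.4% / 6.5% / 5.9% |
| 15 | 0.91 / 0.93 / 0.96 | 7.9% / 7.4% / 6.5% |
| 12 | 0.87 / 0.89 / 0.90 | 9.4% / 8.8% / 8.4% |
| 7.5 | 0.79 in all three | 12.5% to 12.9% |

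A correct paired z test gives 5.7%, so about 0.7 points of each excess come from using z instead of t. With equal SDs the covariate itself adds about 6.5 − 5.7 = 0.8 to 7.9 − 5.7 = 2.2 points. Using t on 76 df with the planned SE still gives 7.6% / 7.0% / 6.3%. The paired t test holds about 5%.

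**Step 6: interval width.** With equal SDs, the mean half-width of the paired t interval against the planned z interval is 5.6 v 5.0, 4.8 v 4.3 and 3.7 v 3.5 WOMAC points, so the paired interval is 13% / 10% / 7% wider. It is about 30% wider if the SD halves. On the SE alone, with equal SDs, the widening is about 10% / 7% / 4% (1/0.91, 1/0.935, 1/0.96).

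**Step 7: check by direct fit.** In one simulated data set, Delta was −11.486 with or without the baseline covariate and with either response. The SE was 2.067 with the covariate and 2.223 without it; the paired SE was also 2.223.

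**Step 8: contrasts between two post-treatment visits.** The baseline row is not in these models. With equal SDs and equal correlations between visits, the SE ratio was 0.99 to 1.00 and type I error was 5.7%, which is the z-for-t effect only.

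**Step 9: site.** One site leaves zero degrees of freedom between sites. The site variance is confounded with the intercept and cannot be estimated. It cancels from a within-patient contrast, so Delta and its SE do not change.

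**The case against.** The strongest reply is that the result depends on choices the plan leaves open. An unconstrained compound-symmetry fit, which allows a negative patient covariance, would restore the paired SE. That is true, but the plan specifies a random patient intercept, and a random-intercept variance is non-negative.

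Second, whether the SE is too small depends on the target. For the mean change conditional on the observed baselines, the planned SE would be too large. The plan, however, defines Delta as the mean change, without conditioning. Reading the model as 12-month rows only does not help: neither the time effect nor the patient intercept would then be identified.

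Third, part of the 7% to 13% widening comes from replacing z with t. This stands; on the SE alone it is about 4% to 10%. The larger range is the cost of the whole fix, which includes the t reference.

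Fourth, the highest type I error figures combine a halved SD with no mean change. A halved SD is more plausible when scores fall towards the floor of the scale, as in the cohort cited in the Rationale (mean total 43 to 8.2 at 12 months). This also stands: with a fall of that size the test result would hardly change, and loss of coverage is the relevant harm. At SD 15 falling to 7.5 with ρ = 0.3, simulated coverage was 87.6%.

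Finally, efficacy is a secondary objective (Section 2.2). That limits the weight of the point but does not correct the interval.

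**Conclusion.** The concern holds. Following the model as written gives an unbiased Delta with complete data, but an SE that is too small for the population mean change, a CI that is too narrow and a test that exceeds 5%. With equal SDs and a correlation of 0.3 to 0.7, the SE is understated by about 4% to 9%. The understatement reaches about 21% if the 12-month SD halves, and nearly vanishes (about 1%) if that SD rises to 18 with a correlation of 0.7. The formula limits it to 29% (√0.5 = 0.71).

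These sizes rest on assumed SDs and correlations, complete data and the non-negative patient variance of a random-intercept model. The finding for post-treatment contrasts was checked only with equal SDs and equal correlations between visits.

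This is a calibration error that should be corrected before analysis; it does not make the analysis invalid. The site term contradicts Section 4 and should be removed, but it adds no weight to the point about the SE.

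**What to change.** In Section 9, Efficacy Analyses:

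1. Take the observed WOMAC score at baseline and 12 months as the response, with visit and severity stratum as fixed effects and a within-patient covariance (unstructured, or a patient intercept).
2. Remove baseline WOMAC as a covariate from any model that includes the baseline row.
3. Remove the random site intercept and the wording on site effects.
4. Define Delta as the 12-month minus baseline contrast and state a t reference. For complete data a paired t analysis (39 df) is equivalent.
5. Apply the same wording to the other baseline-to-visit contrasts. Contrasts between two post-treatment visits can keep the baseline covariate.

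The cost is a change of SAP wording, with no new data. The reported interval becomes wider, by about 7% to 13% with equal SDs.

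### The severity term in the 12-month WOMAC model captures at most half of the KL-group difference in change, and only partly corrects Delta if loss differs by KL group

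*Combined protocol and SAP*

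**What the plan says.** Section 4 (Study Design) sets the size and grouping: "A total of 40 subjects will be enrolled in the single treatment arm", and "The subjects will be stratified according to arthritis severity based on imaging", "with 20 subjects allocated to mild-moderate arthritis based on x-ray" (KL grade 1-2) and another 20 in the severe category (KL grade 3-4).

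Section 9 (Efficacy Analyses) then specifies a linear mixed model for the change in WOMAC to 12 months:

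- Rows: "The baseline and 12 month observations will be included in the model".
- Outcome and covariates: "The dependent variable will be the changes in WOMAC and the independent variables will be the WOMAC at baseline, baseline severity (moderate/severe arthritis").
- Time: "indicators of time (fixed effect" Delta), defined as the mean change in WOMAC.
- Random effects: "random intercepts for patient and site".

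No product of severity, or of baseline WOMAC, with time is listed. The only parameter given a test and an interval is Delta. Other time points are to be handled by the same methods. Section 6 says withdrawn patients are not replaced, and no missing-data method is given for WOMAC.

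**The concern.** A change from baseline is zero at baseline for every patient in both KL groups. A severity main effect in a model with baseline and month-12 rows assumes the same group difference at both times. If the KL groups respond differently, the difference is zero at one time and not at the other, and the single coefficient is a compromise between them.

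Two things are at stake. First, this coefficient is the only severity result the model produces, in a trial that caps enrolment by KL grade. A reader who takes it for the difference in benefit between the groups would understate that difference by at least half. Second, adjusting for severity would ordinarily be expected to hold the pooled change at the enrolled 20:20 mix if one group loses more patients. A main effect in this row structure does so only in part.

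**Working it through.** **Inputs from the documents.** 20 patients per KL group; baseline and month-12 rows; severity and time as main effects; one centre, so the site intercept plays no part. I take the moderate/severe label in Section 9 to be the KL 1-2 versus KL 3-4 grouping of Section 4.

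**Assumed, because the documents give no figures.** Mean 12-month change of -30 (KL 1-2) and -15 (KL 3-4) on the 0-96 total, so a true difference of 15 and a 20:20 target of (-30 - 15)/2 = -22.5; residual SD 16; loss related to KL group only. The plan states no power or effect size for this model, so there is no planned figure to reproduce.

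**Step 1: severity coefficient, complete data.** With two rows per patient, the coefficient of a between-patient covariate depends on the patient's mean over the rows. For a patient with 12-month change D that mean is (0 + D)/2 = D/2. Regressing D/2 on severity and baseline WOMAC gives half the coefficient from regressing D on them: 15/2 = 7.5. With raw WOMAC as the outcome the patient mean is Y0 + D/2; the baseline covariate absorbs Y0 and the half remains. In 20,000 simulated trials (baseline SD 14, slope of change on baseline -0.3) the coefficient averaged 7.54, against 15.07 from a month-12 ANCOVA.

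**Step 2: severity coefficient with loss.** Mixed-model fits to the change outcome put the patient variance at essentially zero, so the least-squares weights apply. Each time point has weight w = n1·n2/(n1 + n2), where n1 and n2 are the two group sizes at that time. The share of the true difference captured is w12/(w0 + w12), with w0 = 20·20/40 = 10.

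| Month-12 completers (KL 1-2 / KL 3-4) | w12 | Share | Coefficient (true 15) |
|---|---|---|---|
| 20/20 | 10 | 10/20 = 0.50 | 7.5 |
| 20/18 | 360/38 = 9.47 | 9.47/19.47 = 0.49 | 7.3 |
| 20/12 | 240/32 = 7.5 | 7.5/17.5 = 0.43 | 6.4 |

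**Step 3: Delta.** Each KL group has weight proportional to n0·n12/(n0 + n12), with n0 = 20 baseline rows and n12 month-12 rows in that group.

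- 20/20: weights 10 and 10; Delta = -22.5, the plain mean.
- 20/18: weights 10 and 9.47; Delta = (10·(-30) + 9.47·(-15))/19.47 = -22.7. The completer mean is (-600 - 270)/38 = -22.9.
- 20/12: weights 10 and 7.5; Delta = (-300 - 112.5)/17.5 = -23.57. The completer mean is (-600 - 180)/32 = -24.38.

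In the 20/12 case the main effect removes (24.38 - 23.57)/(24.38 - 22.5) = 0.81/1.88, about 43% of the shift. Simulation gave -23.61 for the planned model, -24.40 unadjusted and -22.52 for the month-12 ANCOVA with centred covariates.

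**Step 4: bias against sampling error.** In the 20/12 case the SD of Delta from residual error is the square root of (10/17.5)²·256/20 + (7.5/17.5)²·256/12 = 4.18 + 3.92 = 8.10, so 2.85. The bias of 1.07 is 1.07/2.85 = 0.38 of that. Centring to 20:20 gives 0.25·(256/20 + 256/12) = 8.53, an SD of 2.92, so removing the bias costs little precision.

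**The case against.** The plan names one estimand, Delta. Severity is an adjustment covariate; nothing in the documents says its coefficient will be reported, tested or interpreted, and the objectives contain no comparison of efficacy between KL groups. A reader might infer that the trial will publish a halved KL effect, but the documents do not support that. This objection stands. What remains is that the coefficient is easy to misread and that no usable KL-group estimate is planned.

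A reader might also infer that the coefficient is always exactly half the true KL difference. It is half only with complete month-12 data, and then of the baseline-WOMAC-adjusted difference; step 2 shows smaller shares under loss.

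Nor does the severity term fail altogether to protect Delta: step 3 shows partial protection.

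The harm to Delta needs both a KL difference in change and unequal loss. Neither is in the documents, and the larger illustration supposes 40% loss in one group and none in the other. Phone visits for COVID-19 travel restrictions (Section 5) limit one source of loss. These points stand and keep the concern modest.

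Finally, the baseline observation might be meant only as the covariate, with change rows at month 12 alone; severity would then carry the full adjusted difference. But Section 9 states "The baseline and 12 month observations will be included in the model", alongside a time effect that needs two time points. The natural reading is two rows per patient. If the other was meant, the text needs correcting anyway.

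**Conclusion.** The concern holds in a limited form. Under the model as written, the severity coefficient is half the baseline-adjusted KL-group difference in 12-month change with complete data, and less with loss, so it cannot serve as the KL-group effect. This follows from the row structure and does not depend on the assumed effect sizes.

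It would be wrong to conclude that the main efficacy result is invalid. Delta is unaffected with complete data. If both loss and change differ by KL group, the bias in the illustrations runs from about 0.2 points (18 of 20 KL 3-4 patients retained) to about 1.1 points (12 of 20) on a 0-96 scale. Those sizes rest on assumed changes of -30 and -15, no loss in KL 1-2, and loss related to KL group alone. Even the larger bias is under half a standard error and would not overturn a change of that order. The point is worth acting on because a better model is available at almost no cost.

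**What to change.** In Section 9, replace the model by a regression of the month-12 change, with no baseline rows, on baseline WOMAC centred at its mean over all enrolled patients and KL group centred to the 20:20 enrolment. The intercept is then the pooled adjusted change. Alternatively, keep both rows and add severity-by-month-12 and baseline-WOMAC-by-month-12 terms with the same centring, which targets the same quantities. State which rows enter the model, and apply the same form to the other visits.

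Report the pooled adjusted change, and as descriptive estimates the adjusted change in each KL group and their difference, all with t-based 95% CIs. State that these group estimates carry no confirmatory claim.

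The cost is SAP wording and at most two model terms. The per-group intervals will be wide: with SD 16 and 20 patients the standard error is 16/√20 = 3.6, so about ±7 points for a group, and about ±10 for the difference (standard error 16·√(2/20) = 5.1). The pooled interval is slightly wider under unequal loss. The correction assumes that loss depends only on KL group and baseline WOMAC; it does not address loss related to the outcome itself.
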